5.2 Exclusion Criteria

- Known food allergy that could lead to anaphylaxis
- Contraindications to nasogastric tube placement including:
 - Recent midface trauma
 - History of basilar skull fracture
 - Recent ENT surgery
 - Known coagulation abnormalities
 - Esophageal varices and/or esophageal strictures
- Untreated prolapse beyond the hymen
- History of Inflammatory Bowel Disease (does not include IBS)
- Unrepaired rectovaginal fistula/chronic 4th degree laceration
- Full thickness rectal prolapse
- History of congenital anorectal malformation
- History of bowel resection surgery for any indication
- Minor anal procedures within 6 months for treatment of accidental bowel leakage (ABL) (injection of bulking agent or radiofrequency energy) or ligation of hemorrhoids
- Prior pelvic or abdominal radiation
- Diagnosis of cancer of the descending colon or anus

```
FMT for FI
IRB#: 834196
```

- Clinically significant neurological disorders known to affect anal incontinence
- Chronic antibiotic use (>1 month continuous antibiotic)
- Pregnant or planning to become pregnant during the study duration 1 year
 - N/A if participant is not of childbearing potential
- Childbirth within the last 3 months
- Unwilling to use an acceptable form of birth control method if participant is of childbearing potential
 - N/A if participant is of not of childbearing potential
- Participation in another intervention trail impacting bowel function
- Inability to provide informed consent, complete questionnaires independently or to attend intervention sessions
- History of hepatitis C / HIV infection or other immunocompromised condition
- History of bowel resection surgery or pelvic irradiation
- Unable to speak, read, or write in English at a basic level
- In the opinion of the investigator not suitable for participation in the trial

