2.2.1 Assessment for Potential Study Products Drug-Drug Interactions

Potential interaction between the study product and other drug products is currently unknown. As this information is unknown, individuals who are immunocompromised have been excluded from this protocol. Additionally, individuals who have chronic antibiotic use are excluded as investigators are currently unsure if this could potentially be a confounding variable.

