8.1.2 Visit 1: Treatment

At this visit, the study coordinator will collect the one-week BM diary and stool sample from the subject. The PI or another trained physician will meet with the patient. Vital signs will be done to document temperature, blood pressure, heart rate, and oxygen saturation. A nasogastric tube will be placed and secured. The subject will then be escorted to the radiology suite by the study coordinator. A chest x-ray will be performed to ensure adequate placement of the nasogastric tube. The PI or trained physician will confirm adequate placement of the tube with the attending radiologist. The subject will then be escorted back to the office suite by the study coordinator. The PI or trained physician will then administer the treatment. The PMT-002 product will be drawn into a syringe and the syringe will be connected to the nasogastric tube (NGT) and the product will be pushed into the tube until all of the FMT product is administered. The NGT will then be removed by the PI or trained physician. The subject will remain in the office for one hour following the administration of the PMT product.

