9.2 Primary	
Determine if fecal microbial transplantation leads to clinical improvement in refractory fecal incontinence in older women.	Our working hypothesis is that the St. Mark's Vaizey score, a measure of fecal incontinence severity, will significantly improve at 4 weeks after FMT, and will be maintained at 12 weeks, relative to baseline. A secondary outcome will be quality of life at 4 and 12 weeks.
Primary Safety	
Determine the safety of FMT administration via NG tube in older women with FI.	Our hypothesis is that there will be low occurrence of serious adverse events following administration of FMT via NG tube.
Secondary	
Determine whether the effectiveness of microbial engraftment following fecal microbial transplantation is associated with the degree of clinical improvement.	Our working hypothesis is that more transplanted strains will be present at 4 weeks in subjects with a higher response score.
Tertiary	
Determine whether the baseline microbiota configuration affects engraftment in fecal microbial transplantation for fecal incontinence.	Our working hypothesis is that the transplant will be more effective in baseline samples with lower microbial diversity.

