9.4.2 Analysis of Stool Samples

Sequence reads from shotgun metagenomic sequencing will be subjected to quality control, taxonomic assignment, gene function analysis, and metagenomic assembly using the Sunbeam metagenomics pipeline, which was co-written by CHOP Microbiome Center researchers.

The FMT inoculum will be sequenced alongside fecal samples collected from subjects before and after the FMT procedure. DNA sequence reads from the inoculum will be assembled into contigs (overlapping DNA segments) using MEGAHIT (Li Bioinformatics, 2015). The metagenomic contig sequences represent segments of bacterial genomes from the microbiota. We will identify protein coding genes in the contig sequences, and use this gene set as unique identifiers for the genomes in the inoculum. Reads from patients before and after FMT will be aligned to the inoculum marker gene sequences. Gene sequences which are present in patients before the transplant will be removed from the set of inoculum marker genes. The percentage of total non-human reads aligning to the inoculum marker gene set will be used as a measure of bacterial engraftment following FMT.

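### The only antibiotic exclusion is a duration (more than 1 month) with no time window, so a recent or current short course can distort the baseline-diversity and engraftment objectives

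*Combined protocol and SAP*

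**What the plan says.** Antibiotics appear in two places. Section 2.2.1 gives the reason for the rule: "individuals who have chronic antibiotic use are excluded as investigators are currently unsure if this could potentially be a confounding variable". Section 5.2 carries it out as "Chronic antibiotic use (>1 month continuous antibiotic" use. The two agree, since both concern chronic use.

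The baseline stool is collected at home after screening and handed over at the treatment visit, where "the study coordinator will collect the one-week BM diary and stool sample from the subject" (section 8.1.2). No antibiotic condition is attached to that sample or to the week-4 and optional week-12 samples (sections 8.1.4 and 8.1.5).

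The stools serve two objectives, listed in the hypothesis table of section 9:

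- Secondary: "more transplanted strains will be present at 4 weeks in subjects with a higher response score".
- Tertiary: "the transplant will be more effective in baseline samples with lower microbial diversity".

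Section 9.4.2 defines engraftment in two steps. First, "Gene sequences which are present in patients before the transplant will be removed from the set of inoculum marker genes". Then, "The percentage of total non-human reads aligning to the inoculum marker gene set will be used as a measure of bacterial engraftment following FMT".

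A medication log is completed at screening, week 4 and week 12 (sections 8.1.1, 8.1.4 and 8.1.5). Section 9.4 does not use it.

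**The concern.** What matters for these objectives is exposure close to a stool sample or to FMT, and a duration threshold does not measure that. A woman who ends a two-week course the day before her baseline stool passes the criterion. So does one taking a one-week course on the day of FMT.

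The baseline stool does two jobs, so one depleted sample causes two linked errors. It lowers the tertiary predictor, and it changes the marker set that defines the outcome. A course between FMT and week 4 acts on the transplanted strains and blurs the link between engraftment and clinical improvement.

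With 15 women, one or two such samples carry real weight, and the data are meant to inform a later randomised trial. An exposed baseline stool cannot be retaken once FMT has been given.

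**Working it through.** **1. Eligibility text.** Section 5.2 attaches a time window where timing counts: 6 months for minor anal procedures, 3 months for childbirth. The antibiotic line has none. The only other route to exclusion is investigator judgement ("In the opinion of the investigator not suitable for participation in the trial"), which has no antibiotic content.

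**2. Effect on the engraftment measure.** Let D be the inoculum genes and B the genes detected in the woman at baseline. The marker set is M = D minus B, and engraftment is E = reads aligned to M / non-human reads.

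- *Depletion before baseline, then regrowth.* Let S be genes of her own strains that are shared with the donor and fall below detection at baseline. The marker set becomes M plus S, and measured engraftment becomes E + reads aligned to S / non-human reads, which is at least E. Measured baseline diversity is lowered too. Low diversity then goes with high engraftment, as hypothesised.
- *Antibiotic still active at or after FMT.* Donor strains may be suppressed, so reads aligned to M fall. If baseline diversity is also low, low diversity goes with low engraftment, against the hypothesis.

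**3. The plan's own figure.** Section 9.3 gives a detectable engraftment difference of 1.59 SD at a response rate near 60%, that is 9 responders and 6 non-responders. Two-sided alpha 0.05 and a t-test are my assumptions. The noncentrality is 1.59 / √(1/9 + 1/6) = 1.59 / 0.527 = 3.02 on 13 degrees of freedom, and power is 79.6%. The figure reproduces at about 80% power, and nothing in this point changes it.

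**4. Chance of exposure.** The documents give no rate, so I assume p = 2%, 5% and 10%. P(at least one of 15) = 1 − (1 − p)^15 = 26%, 54% and 79%. Expected numbers (15p) are 0.3, 0.75 and 1.5 women.

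**5. Tertiary objective, shift in the hypothesised direction.** Simulation with n = 15 and no true association. Here k women have diversity lowered and engraftment raised by d SD, and a false finding is a two-sided Spearman p < 0.05 with negative sign. The test is my choice, because section 9.4 names none for this objective.

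| Exposed women k | d = 1.5 | d = 2 |
|---|---|---|
| 0 | about 2.5% | about 2.5% |
| 1 | 4.9% | 6.0% |
| 2 | 8.5% | 12.7% |
| 3 | 13.1% | 22.2% |

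These rows are conditional on k. The planning figure averages them over the binomial distribution of k. At p = 5% the weights for k = 0, 1, 2, 3 are 0.463, 0.366, 0.135 and 0.031:

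- d = 1.5: 0.463 × 2.5 + 0.366 × 4.9 + 0.135 × 8.5 + 0.031 × 13.1 = 4.5%
- d = 2: 0.463 × 2.5 + 0.366 × 6.0 + 0.135 × 12.7 + 0.031 × 22.2 = 5.8%

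The small remaining weight (k of 4 or more) adds 0.1 to 0.2 points. The averages are about 3–4% at p = 2%, 5–6% at 5% and 7–11% at 10%.

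**6. Same simulation, engraftment shifted down.** With one to three exposed women, false findings in the hypothesised direction fall below about 1%, and those in the opposite direction rise to 5–22%.

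**7. Secondary objective.** Simulated with 9 versus 6 and a true difference of 1.59 SD. If two women chosen at random have measured engraftment inflated by 1 or 2 SD, power falls from about 80% to about 75% or 62%.

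**The case against.** **It is a small pilot and these are lower-tier aims.** True. Primary efficacy, safety and sample size are untouched. That limits the weight of the point but does not remove it, because the microbiome data are a stated product of the study.

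**Exposed women can be found from the medication log, and the investigator can exclude them.** The log makes a check possible, but no rule calls for one. Discretion without a criterion may be applied unevenly.

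**The rule may sit elsewhere.** Section 8.1.1 refers to separate stool-collection instructions and section 10.1.6 to Manuals of Procedures, neither of which is available here. This stands: the claim covers the protocol text only.

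**The size is assumed.** This also stands. The rates, the shifts, their equality in both variables and the test are mine.

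**Low diversity caused by antibiotics might truly favour engraftment.** That would be an instance of the tertiary hypothesis, though with a different cause. Without an exposure rule, the analysis cannot separate it from the regrowth artefact.

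A reader might also infer two stronger textual faults:

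- *That section 2.2.1 promises to exclude all antibiotic users and section 5.2 fails to deliver.* It does not: section 2.2.1 speaks of chronic use only and of uncertainty about confounding.
- *That a long course years ago would exclude a woman.* This is strained: section 5.2 uses explicit words for past exposure where it counts, as with bowel resection or radiation, and uses none here.

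**Conclusion.** The gap is real in the protocol text, and the route to bias follows from the plan's own engraftment definition. The right wording is that it can distort the two microbiome objectives, since distortion requires an exposed woman to enrol.

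It is tempting to say that the bias always favours the hypothesised result. The documents do not support that: the sign depends on whether exposure precedes baseline only or continues to FMT and beyond.

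The size is illustrative. The average false-finding rate of about 3–11% assumes that every exposed woman shifts in the hypothesised direction. The 13–22% figures apply only if three women are exposed, which is more than the 0.3 to 1.5 expected under the same assumptions. The change should be made, but it is not critical to the trial's main conclusion.

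**What to change.** **Section 5.2.** Keep the chronic-use exclusion. Add a time-bound criterion: no systemic antibiotic of any duration within a stated window before the baseline stool and up to FMT. The sponsor should set the length, since the documents give no basis for one.

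**Section 5.4 and the schedule of activities.** State that a woman inside the window is deferred, not screen-failed, and gives her baseline stool after it ends. Section 5.4 bars rescreening of women who fail the criteria, so it needs this exception. If deferral takes the interval from screening to treatment past 30 days, the schedule's repeat-test rule applies.

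**Section 9.4.** Pre-specify that stools exposed to systemic antibiotics, including those taken between FMT and week 4 or week 12, are flagged from the medication log, and that the engraftment analyses are repeated without them.

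**Cost.** One added criterion, one exception to the rescreening bar, some repeat tests, slightly slower accrual, and one further analysis on fewer samples from data already collected. N = 15 is unchanged.

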5.3 Lifestyle Considerations

After administration of the investigational product (PMT-002) there is no way for investigators to stop or retrieve the product from the subject. Additionally, it is unknown how long the product will remain in the subject's body; thus, subjects should be fully informed that withdraw of the investigational product is not possible and be comfortable with this information prior to administration. Furthermore, as this is a first in human trial for the indication of FI unforeseen side effects are expected.

5.4 Screen Failures

Screen failures are defined as participants who consent to participate in the clinical trial but are not subsequently administered the study intervention or entered in the study. A minimal set of screen failure information is required to ensure transparent reporting of screen failure participants, to meet the Consolidated Standards of Reporting Trials (CONSORT) publishing requirements and to respond to queries from regulatory authorities. Minimal information includes demography, screen failure details, eligibility criteria, and any serious adverse event (SAE).

Individuals who do not meet the criteria for participation in this trial (screen failure) because of inclusion/exclusion criteria for this protocol are not eligible for rescreening.

5.5 Strategies for Recruitment and Retention

Clinical Practices of Investigators

Women presenting to the clinical practices of the Hospital of the University of Pennsylvania Health System Division of OB GYN (Urogynecology) for consultation/complaint or indication for FI (after clinical confirmation of their potential eligibility for admission into the study based on inclusion and exclusion criteria) will be approached to participate by the principal investigator (PI) or providing physician, in addition to the study coordinator. In the recruitment visit, study details including the intervention will be explained. Risks and benefits will be thoroughly discussed and consents given to the patient prior to any study procedures being performed.

Hospital/Local Health Care Referrals

Subjects will be recruited at each site from individual practice(s) of the investigators as noted above as well as faculty/resident clinics. Ongoing contact with practice and faculty members as well as with residents will be made by the investigators and coordinators, reminding them of the inclusion criteria, importance of the study, etc. In addition, the investigators will describe the study to members of other departments in the hospital, primarily family practice, medical endocrinology, and gynecology who also see and treat these patients. Contact with local physicians will be made and/or grand rounds will be given to disseminate information about the study. Letters will be mailed to potential subjects, which provides details of the study and contact information of the study team (to allow for subject to reach out for more information). Penn Datastore may be utilized to provide a list of potential subjects based on clinical practice information.

Referrals from Study Participants

Study participants often refer friends, acquaintances, and colleagues to be potential participants. The investigator will let the patient know that they can refer others to be considered for participation in the study.

Previous Study Participants

The trial will be offered to women who have previously participated in clinical trials offered by the study team, who have consented to be contacted for future participation via their preferred contact method (after confirmation of their potential eligibility for admission into the study based on inclusion and exclusion criteria).

Web sites

The study will be prominently displayed on the local Penn website. Information will also be available at clinicaltrials.gov. Social media and Craigslist will also be utilized, as this has been a proven source of recruitment in the past. Ads placed on social media, specifically Facebook and Instagram, will be one-way ads and the study team will not directly interact with subjects on

social media. The ads will highlight a contact number for the interested individual to call to discuss the study. Social media ads will be monitored by the University of Pennsylvania study coordinator to ensure they are being properly featured and not causing inappropriate comments. This monitoring will occur bi-weekly. If any problems arise with the social media ads they will be immediately removed, however, this is not anticipated as they are one-way ads. This type of advertising has been previously used for studies within the department and has been well received.

Institutional Review Board (IRB) Approval

It is expressly acknowledged that all informational material that could be construed to be advertising will be approved by the central IRB prior to dissemination.

6 STUDY INTERVENTION

6.1 Study Intervention Administration

6.1.1 Study Intervention Description

Fecal microbiota transplantation (FMT) is a treatment that involves administration of minimally manipulated microbial community from stool of a healthy donor into the patient's intestinal tract. Clinically, FMT is performed with the intent of restoring normal function of the gut microbiota (Khoruts, 2016).

6.1.2 Dosing and Administration

A single dose of PMT-002 will be administered via a gastroduodenal tube over 10 to 90 minutes (target 30 minutes). In brief, nasogastric duodenal tube will be placed by a physician and its location will be checked by X-Ray. Once placement is confirmed, the PMT-002 product will be delivered via the NGT using a syringe attached to the end of the tube. Once the product has been delivered, the NGT will be removed. The patient will be observed for 1 hour in the office for potential adverse events.

6.2 Preparation/Handling/Storage/Accountability

6.2.1 Acquisition and accountability

Following the screening and consent visit, the lab director at the PMT manufacturing facility at the University of Pennsylvania will be notified of the date for visit 1 (FMT visit) to ensure the investigational product will be available for that date. On the day of the Study visit, study personnel will obtain the PMT product from the manufacturing facility and transport it to the office where it will be administered. The PMT-002 will be packaged on dry ice from the PMT manufacturing facility. The time of release from frozen storage will be documented and included in PMT product packaging. Upon receipt of the product by the Investigator, packaging will be inspected for integrity, and the product will be checked to ensure that it is still frozen and logged

in the investigational product accountability log. The investigational product label will also be checked to ensure that the proper product is received, and to ensure that the product has not expired.

The volume of investigational product will be recorded at the time of drug product manufacturing, and the volume of residual investigational product (if any) will be recorded by the licensed medical professional performing administration after administration is completed (or stopped). Any remaining investigational product will be disposed of at the clinical site.

6.2.2 Formulation, Appearance, Packaging, and Labeling

PMT-002 is composed of donor stool, glycerol, and saline contained in cryobags and labelled (according to FDA regulations 21CFR312.6) for upper GI use. These cryobags will also be labeled with a unique color label to facilitate identification as a PMT-002 drug product.

The potency of each PMT-002 is $1 \times 10^8 - 10^{12}$ CFU/dose (1 dose per cryobag), based on Quantitative Anaerobic Culture from Fecal Filtrate. The appearance of the PMT-002 is frozen aqueous solution within the product container is properly labeled, free of defects. Prior to release of the drug product, all serological, stool and multi-drug resistant organism (MDRO) testing will be confirmed to be negative.

6.2.3 Product Storage and Stability

PMT-002 drug product should be stored as detailed on the investigational product labeling, prior to release to site.

The investigational products are transported frozen on dry ice by courier or study staff to the clinical location. Investigational products are transported in containers labelled and maintained at a temperature in accordance with federal and local regulations for the transport of biological products.

At the clinical location, administration of PMT-002 should be initiated within 180 total minutes of product release from frozen storage by the manufacturer.

PMT-002 doses will be thawed at room temperature for 30-60 minutes prior to administration.

Any doses released from frozen storage but not administered within the allotted time (180 minutes) after release (e.g., due to delays in transport) should be destroyed. In such cases, eligible subjects should be offered another dose, and the release process should be re-initiated.

